### **3.8. Analysis Visit Windows**

#### **3.8.1. Definition of Study Day**

Study day will be calculated from the first dosing date of study drug and derived as follows:

- For postdose study days: Assessment Date – First Dosing Date + 1

- For days prior to the first dose of study drug: Assessment Date – First Dosing Date

Therefore, Study Day 1 is the day of first dose of study drug administration. Please note that this differs by 1 day relative to days specified within the protocol.

### 3.8.2. Analysis Visit Windows

Participant visits might not occur on protocol-specified days. Therefore, for the purpose of analysis, observations will be assigned to analysis windows. A notable exception to the analysis visit windows below is the end of treatment/date of delivery. This will be summarized as its own visit and that will be the value used for endpoints that look at either the value or change from baseline to delivery.

The analysis windows for ItchRO, sBA, hematology, chemistry, coagulation, weight, vital Signs, and urinalysis are provided in [Table 2](#).

The analysis windows for 5-D Itch, EQ-5D-5L, PROMIS Fatigue and Sleep patient reported outcomes (PROs), PIS-Itch, PGIC-Itch, and Biomarker samples (7 $\alpha$ -hydroxy-cholesten-3-one [7 $\alpha$ C4], fibroblast growth factor 19 [FGF-19], autotaxin, progesterone sulfate, and glucagon-like peptide 1 [GLP-1]) are provided in [Table 3](#).

The analysis windows for lipid panel and glycated albumin are provided in [Table 4](#).

The analysis windows for vitamin A, D, and E levels and fetal ultrasound are provided in [Table 5](#).

**Table 2 Analysis Visit Windows for ItchRO^, sBA, Hematology\*, Chemistry\*, Coagulation\*, Weight, Vital Signs, and Urinalysis**

Nominal Visit	Nominal Study Day	Lower Limit	Upper Limit
Baseline	1	(none)	1
Week 1	8	2	11
Week K (K is every week after previous visit)	K*7 + 1	K*7 – 2	K*7 + 4

^ ItchRO is collected daily, but will have weekly averages calculated and results will be grouped according to the analysis windows above.

\* Hematology, chemistry, and coagulation are not planned to be collected at the baseline visit. Rather, the screening visit (or a subsequent unscheduled visit) will serve as the baseline.

**Table 3 Analysis Visit Windows for 5-D Itch, CSS, EQ-5D-5L, PROMIS Fatigue and Sleep PROs, PIS-Itch, PGIC-Itch, and Biomarker Samples (C4, FGF-19, Autotaxin, Progesterone Sulfate, GLP-1)**

Nominal Visit	Nominal Study Day	Lower Limit	Upper Limit
Baseline*	1	(none)	1
Week 3	22	19	25

\*PGIC-Itch was not collected at baseline.

**Table 4 Analysis Visit Windows for Lipid Panel and Glycated Albumin**

Nominal Visit	Nominal Study Day	Lower Limit	Upper Limit
Baseline	1	(none)	1
Week 2	15	2	22
Week K (K is every 2 weeks after previous visit)	$K*7 + 1$	$(K - 1)*7 + 2$	$(K+1)*7 + 1$

**Table 5 Analysis Visit Windows for Vitamin A, D, and E Levels and Fetal Ultrasound**

Nominal Visit	Nominal Study Day	Lower Limit	Upper Limit
Baseline	1	(none)	1
Week 4	29	2	43
Week K (K is every 4 weeks after previous visit)	$K*7 + 1$	$(K - 2)*7 + 2$	$(K+2)*7 + 1$

### 3.8.3. Selection of Data in the Event of Multiple Records in an Analysis Visit Window

Depending on the statistical analysis method, single values may be required for each analysis window. For example, change from baseline by visit usually requires a single value, whereas a time-to-event analysis would not require 1 value per analysis window.

If multiple valid, nonmissing, continuous measurements exist in an analysis window, records will be chosen based on the following rules if a single value is needed:

- In general, the baseline value will be the last nonmissing value on or prior to the first dose of study drug, unless specified differently. If multiple measurements occur on the same day, the last nonmissing value prior to the time of first dose of study drug will be considered as the baseline value. If these multiple measurements occur at the same time or the time is not available, the average of these measurements (for continuous data) will be considered the baseline value.

- For postbaseline values:
  - The record closest to the nominal day for that visit will be selected.
  - If there are 2 records that are equidistant from the nominal day, the later record will be selected.
  - If there is more than 1 record on the selected day, the average will be taken, unless otherwise specified.
  - If a participant gives birth prior to Week 3, then the value obtained at the date of delivery will be analyzed according to the next analysis window after the previous visit. For example, if there was a Week 2 sample provided on Day 15 and then the participant delivered on Day 18, the Day 18 record would be mapped to Week 3, even though it is contained within the upper bound of the Week 2 analysis window. This is designed to minimize the amount of missing data for the primary endpoint.

If multiple valid, nonmissing, categorical measurements exist in an analysis window, records will be chosen based on the following rules if a single value is needed:

- For baseline, the last available record on or prior to the date of the first dose of study drug will be selected. If there are multiple records with the same time or no time recorded on the same day, the value with the lowest severity will be selected (e.g., normal will be selected over abnormal for safety electrocardiogram [ECG] findings).
- For postbaseline visits, if there are multiple records with the same time or no time recorded on the same day, the value with the worst severity within the window will be selected (e.g., abnormal will be selected over normal for safety ECG findings).

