Visit Name	Screening	Treatment Period				Follow-Up		Notes
		Baseline	Weeks 1, 2, 3, etc.	Early Termination*	EOT/Delivery	F1	F2 (EOS)	
Day/Week (Window)	Day -10 to -1	0*	Every 7 Days (±1 Day) Until Delivery		Day of Delivery (+2 Days)	Phone Call: 14 Days after Delivery (±3 Days)	Clinic Visit: 28 Days after Delivery (±3 Days)	
*Participants who early terminate from study drug should still continue with weekly visits through delivery, F1, and F2.
 
Some visits may be conducted as a home health or remote visit at the discretion of the investigator upon approval by the sponsor or designee and in accordance with local and regional regulations.
 
*See Section 8.1.8 for further details on timing of baseline visit.

sBA	X	X*	X*	X	X**		X	
At each visit except EOT/Delivery, sBA should be drawn 30-90 minutes postprandially, whenever possible). Every effort should be made to collect sBA levels at approximately the same time of day (morning, midday, or afternoon) at each visit starting with baseline, except for EOT/delivery.
 
*At baseline and Week 3, there will be 2 samples collected.
 
**At EOT/Delivery, there will be 2 samples collected, without regard to last meal.

Postprandial biomarker samples (maternal) 
 
• 7<math>\alpha</math>C4 (postprandial, 30-90 minutes)
 
• FGF-19
 
• Autotaxin
 
• Progesterone sulfate
 
• GLP-1
 
		X	X*		X			
Prior to the sample collection, all participants are strongly encouraged to eat a meal within approximately 30-90 minutes (whenever possible). Every effort should be made to collect biomarker sample collection at approximately the same time of day (morning, midday, or afternoon) at each visit.
 
*At Week 3 visit only

5-D Itch; Adult Itch RO; 7 $\alpha$ C4=7 $\alpha$ -hydroxy-cholesten-3-one; AE=adverse event; BPP=biophysical profile; CRL=crown rump length; CSS=Clinician Scratch Scale; CTG=cardiotocography; eCRF=electronic case report form; eDiary=electronic diary; EDC=electronic data capture; EOS=end of study; EOT=end of treatment;

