For participants with ICP, the reduction of sBA provides an opportunity to address both the significant burden of maternal pruritus as well as reduce the high rate of fetal morbidity and mortality. Pharmacological inhibition of IBAT has demonstrated a reduction in sBA and pruritus across multiple clinical studies involving cholestatic liver diseases (Hegade et al. 2017; Thompson et al. 2019; Bowlus et al. 2019; Gonzales et al. 2019a, 2019b; Mayo et al. 2019). Evidence from other IBAT inhibitors in cholestatic diseases supports the rationale that volixibat has the potential to lower total sBA concentrations in women with ICP and impact pruritus and other comorbidities of ICP. In clinical studies, volixibat demonstrated a consistent ability to reduce systemic bile acids, as evidenced by rapid and significant fecal excretion and consistent changes in markers, indicative of an interruption in the enterohepatic recirculation of bile acids. In Phase 1 studies, in instances where participants demonstrated elevated baseline levels of sBA, rapid and significant decreases were observed on volixibat treatment, consistent with findings from a nonclinical model of mild cholestasis.

Peak sBA levels are associated with risk of adverse perinatal outcomes; for this reason, nonfasted (i.e., postprandial) sBA levels are clinically useful for monitoring ICP because they typically reflect higher levels compared with fasting values (Geenes et al. 2014; Oruc et al. 2014). Collection of samples 30–90 minutes postprandially would be expected to capture peak serum levels in most patients (Lundasen et al. 2006).

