### **8.1.9. Baseline Visit**

The baseline visit should occur in the morning, whenever possible. After eligibility for randomization is confirmed, the following assessments must be performed in order; please refer to the SoA (Table 1) for details.

1. PRO assessments
2. Nonfasting (e.g., postprandial) blood draw for sBA and other laboratories, per the SoA
3. First dose of study drug under direct observation, with fetal monitoring pre- and post-dose (see Section 8.4.2 for details). The first dose of study drug must be administered only after the sBA blood draws have been completed.

Note: Participants may have the option to complete the baseline visit PRO assessments (i.e., 5D-itch scale, CSS, EQ-5D-5L, PROMIS SF v1.0-Fatigue 7a, PROMIS SF v1.0-Sleep Disturbance, PIS-Itch) at home before they arrive onsite for the baseline (Day 0) visit.

Timing of other required procedures at the baseline visit is at the investigator's discretion.

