Vitamin A, D, and E levels		X	X*		X		X	*Every 4 weeks, starting with Week 4 visit. The sample collection tube should be protected from light.
Urinalysis	X	X	X	X	X		X	
Lipid panel, glycated albumin	X		X*		X		X	*Every 2 weeks, starting with Week 2 visit
sBA	X	X*	X*	X	X**		X	At each visit except EOT/Delivery, must be drawn in the non-fasting state (e.g., postprandially), 30-90 minutes after start of a meal. Every effort should be made to collect postprandial sBA levels at approximately the same time of day (morning, midday, or afternoon) at each visit starting with baseline, except for EOT/delivery.  *At baseline and Week 3, an additional fasting sBA must be performed.  **At EOT/Delivery, sBA may be performed without regard to last meal.
AE review		X	X	X	X	X	X	AEs for mother and baby to be collected and reviewed for up to 30 days after respective dates of hospital discharge.

Visit Name	Screening	Treatment Period				Follow-Up		Notes
		Baseline	Week 1, 2, 3, etc.	Early Term*	EOT/Delivery	F1	F2 (EOS)	
Day/Week (Window)	Day -10 to -1	0*	Every 7 Days (±1 Day) Until Delivery		Day of Delivery (+2 Days)	Phone Call: 14 Days after Delivery (±2 Days)	Clinic Visit: 28 Days after Delivery (±3 Days)	
*Participants who early terminate from study drug should still continue with weekly visits through delivery, F1, and F2.
 
Some visits may be conducted as a home health or remote visit at the discretion of the investigator upon approval by the medical monitor or designee and in accordance with local and regional regulations.
 
*Regardless of date of screening visit, baseline visit must occur no later than 35 weeks and 0 days gestational age.

Fetal ultrasound	X*	X*	X*					*Every 4 weeks while on study treatment; first ultrasound may be done during screening OR baseline (both are not required)
Antepartum fetal monitoring (NST/CTG or BPP)		X*	X*					*At baseline and Week 1 visits only, and thereafter at the discretion of the investigator

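### SAP 3.8.3 takes a single sBA sample at baseline but an average at Week 3, the only two pre-delivery visits with paired samples, and nothing names the endpoint sample

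*SAP*

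**What the plan says.** **Samples.** Protocol Table 1 states in its sBA row: "At baseline and Week 3, there will be 2 samples collected". It does not say how the two differ. The SAP's own schedule (Appendix 1, Table 7), which follows protocol Version 1, has a postprandial sample at each visit before delivery and adds: "At baseline and Week 3, an additional fasting sBA must be performed". Weeks 1 and 2 have one scheduled sample.

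**Selection rule.** SAP 3.8.3 sets the baseline value as follows: "If multiple measurements occur on the same day, the last nonmissing value prior to the time of first dose of study drug will be considered". There is one exception, under which the mean is used: "If these multiple measurements occur at the same time or the time is not available, the average of these measurements". For post-baseline visits the rule is "If there is more than 1 record on the selected day, the average will be taken, unless otherwise specified".

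**Which baseline samples qualify.** Both do. Protocol 8.1.9 says: "The first dose of study drug must be administered only after the sBA blood draws have been completed". Protocol 8.6 has the time of each draw entered in the eCRF, so the exception for missing times should seldom apply.

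**Override.** The averaging rule gives way to a specific instruction, but there is none for sBA. SAP 6.1.1 and 6.1.2 and protocol 10.4.1.1 define the endpoint without naming a meal state or a first, last or mean sample.

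**Meal state.** Protocol 4.3.2.1 prefers postprandial values because peak sBA tracks perinatal risk and because "they typically reflect higher levels compared with fasting values".

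**Delivery.** Protocol Table 1 takes two samples at delivery whatever the meal timing. For births before Week 3, SAP 3.8.3 assigns the delivery value to the next analysis window, which can be Week 3.

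**The concern.** The two visits that define the primary endpoint are the only scheduled visits before delivery where the same-day rule has work to do, and it works differently at each. Read literally with the SAP's schedule, baseline is one sample, Weeks 1 and 2 are single postprandial samples, and Week 3 alone is a fasting/postprandial mean. The change score then subtracts unlike quantities.

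At stake are the within-arm LS mean changes and their tests against zero (protocol 10.4.1.1, SAP 6.1.2), the weekly profile, any sBA responder analysis, and any open-label arm read without a placebo comparison. A confirmatory primary variable should also not depend on a sample choice that could be settled after data have been seen.

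**Working it through.** **1. The plan's own figure.** Inputs from protocol 10.1 and SAP 1.3: 100 per arm, difference 10, SD 25, two-sided alpha 0.05. No unit is stated; µmol/L is assumed.

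- Standard error = 25 × √(2/100) = 3.536, and 10 / 3.536 = 2.828.
- Power ≈ Φ(2.828 − 1.960) = 80.7% (80.4% with the noncentral t). The stated 80% is reproduced. Here it serves mainly to fix 10 as the yardstick.

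**2. The rule traced through the SAP's schedule.**

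- Baseline, two timed samples: the last one only.
- Weeks 1 and 2, one postprandial sample: that value.
- Week 3, two samples on one day: their mean.

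**3. Within-arm shift with no true change.** Let P be the postprandial level and P − g the fasting level. The documents give no value for g.

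- Week 3 value = (P + P − g)/2 = P − g/2.
- Last baseline sample postprandial: change = (P − g/2) − P = −g/2.
- Last baseline sample fasting: change = (P − g/2) − (P − g) = +g/2.
- In either case the profile drops by g/2 between Week 2 (P) and Week 3 (P − g/2).

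For assumed g of 5, 10, 20 and 30, the size of the shift is 2.5, 5, 10 and 15, against a planned difference of 10.

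**4. The Part 2 contrast.** The same rule applies in both arms. If g is the same in both, the shift subtracts out. Baseline sBA is also a covariate in the MMRM, so modelling the change or the Week 3 value gives the same treatment contrast, and the baseline choice moves only the baseline coefficient. If the drug has no effect on either sample, the arms have the same Week 3 distribution under any selection rule, so type I error is not inflated.

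The contrast changes only if the drug effect differs by meal state. With a postprandial effect of 10 and a fasting effect of f × 10, the analysed effect is 10(1 + f)/2:

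- f = 0.75 gives 8.75
- f = 1 gives 10
- f = 1.25 gives 11.25

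The documents give no value for f, so the direction is unknown. Averaging at both visits would not remove this effect, because it comes from mixing meal states at Week 3.

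**5. If both samples are nonfasting and separately timed.** There is no gap and no bias. Let w be the within-day variance of one sample, and let 625 = V + 2w be the change-score variance with one sample at each end. One sample at baseline and a mean at Week 3 gives V + 1.5w; means at both ends give V + w. For 2w equal to 0 to 30% of 625 (assumed), power is 80.7 to 83.7% with the mixed rule and 80.7 to 86.6% with means at both ends. At the 30% end, w = 93.75 and V = 437.5, so the SDs are √578.1 = 24.04 and √531.25 = 23.05. Nothing is lost against the plan; up to 2.9 points are forgone. This is a simple change-score calculation that ignores baseline adjustment.

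**6. If both samples share a collection time.** The exception averages them at baseline too, and the mismatch disappears.

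**The case against.** The strongest reply is that the harm joins two designs. The fasting sample stands only in the SAP's schedule. The current protocol asks for postprandial draws where possible, specifies a nonfasting draw at baseline, and does not call the second sample fasting. An open-label Part 1 without placebo stands only in the current protocol; in the SAP's design the Part 1 primary cohort has a placebo arm, and the formal interim analysis uses that cohort alone.

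This largely stands. A reader might infer that the rule overstates the Week 3 fall in the current open-label Part 1 and so distorts dose selection. The documents do not support that. It needs one feature from each version, the sign reverses if the last baseline sample is fasting, and a shift common to two concurrently randomised doses cancels between them. What survives is that the SAP holds the only selection rule and still carries the fasting schedule. Within that version, the open-label supplemental cohort (up to 30 participants, no placebo, an analysis that may inform dose selection) is directly exposed.

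Two further replies also stand. The two samples may be tubes from one draw; protocol 8.1.9 uses both singular and plural. And restricting every visit to postprandial samples would discard delivery values that SAP 3.8.3 deliberately maps to Week 3 to limit missing primary data.

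**Conclusion.** The inconsistency in SAP 3.8.3 is real, and the primary variable is not uniquely defined. Under the SAP's schedule, within-arm Week 3 changes shift by −g/2 or +g/2 according to which baseline sample came last. That is 2.5 to 15 for assumed gaps of 5 to 30, and the gap itself is not in the documents. Under the current protocol the consequence ranges from some forgone precision (separately timed nonfasting samples) to nothing (one shared collection time).

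A reader might infer that the Part 2 test is biased or loses power. The documents do not support this. The contrast is unaffected when the gap is equal in both arms, type I error is not inflated, and a loss of power would require a smaller drug effect on fasting sBA, for which no evidence is given. This is a gap in the endpoint definition to close before unblinding, not a threat to the validity of the primary test.

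**What to change.** 1. Add an sBA-specific rule to SAP 3.8.3 and 6.1.1. It should name the scheduled endpoint sample (the postprandial one, in line with protocol 4.3.2.1) and apply the same same-day rule at baseline and at every post-baseline visit. Where two like samples exist, use their mean at both visits.
2. Do not average a fasting sample with a postprandial one. Summarise fasting values separately.
3. Keep the mapping of delivery samples for births before Week 3 as an explicit exception, with a sensitivity analysis that excludes those values.
4. Reconcile SAP Appendix 1 with protocol Table 1 on what the two samples are, and label them.

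The cost is SAP wording and a label in Table 1, with no new samples. The downside is an occasional missing visit where only a fasting sample exists. Postprandial timing is sought only where possible, and the protocol mentions recording draw times but not meal state. The rule should therefore follow the scheduled sample label; a rule based on actual meal timing might need an extra eCRF field.

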## **4. PARTICIPANT DISPOSITION**

### **4.1. Participant Enrollment and Disposition**

A summary of participant enrollment will be provided by treatment group for each investigator and overall. The summary will present the number and percentage of participants enrolled. For each column, the denominator for the percentage calculation will be the total number of participants analyzed for that column.

A similar enrollment table will be provided by randomization stratum. The denominator for the percentage of participants in the stratum will be the total number of enrolled participants. If there are discrepancies in the value used for stratification assignment between the IXRS and the clinical database, the value collected in the clinical database will be used for the summary. A listing of participants with discrepancies in the value used for stratification assignment between the IXRS and the clinical database at the time of data finalization will be provided.

The randomization schedule used for the study will be provided as an appendix to the CSR.

A summary of participant disposition will be provided by treatment group and part (Part 1 [double-blind], Part 2 [double-blind], and Open-Label). This summary will present the number of participants screened, the number of participants who met all eligibility criteria but were not randomized with reasons participants not randomized, the number of participants randomized, and the number of participants in each of the categories listed below:

- Safety Analysis Set
- Intent-to-Treat
- Modified Intent-to-Treat
- Per-Protocol Analysis Set
- Continuing study drug
- Completed study drug
- Did not complete study drug with reasons for premature discontinuation of study drug
- Continuing study
- Completed study phase
- Did not complete the study phase with reasons for premature discontinuation of study

For the status of study drug and study completion and reasons for premature discontinuation, the number and percentage of participants in each category will be provided. The denominator for the percentage calculation will be the total number of participants in the Safety Analysis Set corresponding to that column. In addition, a flowchart will be provided to depict the disposition.

The following by-participant listings will be provided by participant identification (ID) number in ascending order to support the above summary tables:

- Reasons for premature study drug or study discontinuation
- Lot number

#### **4.2. Extent of Study Drug Exposure and Adherence**

Extent of exposure to study drug will be examined by assessing the total duration of exposure to study drug and the percent of study drug dose received as specified in the protocol.

##### **4.2.1. Duration of Exposure to Study Drug**

Total duration of exposure to study drug will be defined as last dosing date minus first dosing date plus 1, regardless of any temporary interruptions in study drug administration except for protocol-specified dose holds and/or dose reductions, and will be expressed in weeks using up to 1 decimal place (eg, 4.5 weeks). If the last study drug dosing date is missing, the latest date among the study drug end date, clinical visit date, laboratory sample collection date, and vital signs assessment date will be used.

The total duration of exposure to study drug will be summarized using descriptive statistics and using the number (ie, cumulative counts) and percentage of participants exposed through the following time periods: 1 day, 3 weeks, 6 weeks, 9 weeks, 12 weeks, 15 weeks, 18 weeks, and >18 weeks. Summaries will be provided by treatment group for the Safety Analysis Set.

No formal statistical testing is planned.

A listing of exposure to the study drug will be provided.

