With regard to BID versus QD dosing, a prior volixibat study (SHP626-101) demonstrated improved fBA excretion with BID dosing compared with QD dosing for an equivalent daily exposure (i.e., mean fBA excretion was greater for 5 mg BID compared with 10 mg QD). BID dosing provides greater coverage of IBAT over a 24-hour period, supporting the likelihood of relatively increased efficacy with a BID dosing schedule. Based on modeling, predicted GI lumen concentrations of volixibat are expected to provide full IBAT inhibition for ~12 hours following a 20-mg dose; thus, 20 mg BID would be expected to provide 24-hour coverage of the IBAT transporter on average. BID dosing has also been shown to result in greater treatment effects with another IBAT inhibitor, maralixibat, where improvements in sBA and pruritus were observed when the dose regimen was doubled from QD to BID in pediatric cholestasis.

Based on available safety, tolerability, and PD data, and further supported by data demonstrating only sporadically detectable volixibat concentrations (with most below the LLOQ) in human plasma at the doses proposed, 20-mg BID and 80-mg BID are likely to represent an appropriate range of lower and higher dosages to study in Part 1 for treatment effects while being well tolerated and maintaining an acceptable safety profile in ICP for participants and fetuses. Although 20 mg BID and 80 mg BID are the initial dosages, a dose reduction of up to 75% of the original assigned dose, as outlined in [Section 6.2](#), may also provide the opportunity for de facto

exploration of 3 additional dosages (i.e., 5 mg BID, 10 mg BID, and 40 mg BID) in Part 1, should dose reductions be warranted for safety or tolerability considerations in some participants. Based upon thorough review of dose/exposure/response relationships for all doses explored in Part 1 at the interim analysis, an appropriate dose for Part 2 will be selected.

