## 6.2. Dose Modification

If a participant experiences an SAE believed to be related to study drug or a Grade 3 AE believed to be related to study drug, temporary interruption of dosing should be considered; see [Section 7.1](#) for additional information on situations requiring permanent discontinuation of study drug. When possible, the medical monitor should also be notified within 24 hours after any treatment-related AE that is Grade  $\geq 3$ . Dose interruptions for Grade 1 or Grade 2 AEs, including diarrhea, may be permitted in limited situations if the investigator deems it medically appropriate (e.g., prolonged symptoms with no response to adjunctive treatment, intolerance of AEs to the point that participant is considering early termination from study, etc.). In general, rechallenge (i.e., resumption of dosing) may be considered for an AE if an alternative cause for the event is discovered or the event has resolved or returned to baseline severity; any concerns regarding rechallenge should be discussed with the medical monitor. If a participant experiences an SAE or a Grade 3 AE believed not to be related to study drug, temporary interruption of study drug or dose reduction may still be considered with medical monitor or sponsor designee approval.

A dose reduction of up to 75% of the original assigned dose is permitted in a stepwise reduction. For example, if any one of the following criteria are met, a dose reduction of up to 50% is allowed and then another reduction to 25% of original dose level may occur:

- $\geq 1$  episode of treatment-related cramping/abdominal pain requiring an unscheduled visit for threatened preterm labor
- Any treatment-related GI AE resulting in secondary dehydration and/or hospitalization
- For any participant who complains of intolerability to study drug that results in consideration of withdrawal from study drug, a dose interruption or reduction should be offered prior to early discontinuation from treatment.
- Dose reductions for events not meeting the above criteria are generally not recommended but may be permitted in limited situations with approval from the medical monitor.

For Part 2, all dose modifications and rechallenges will be performed in a blinded manner.

Upon satisfactory resolution of the event(s) driving the dose modification as deemed by the investigator, rechallenge with the original dose level may be considered. All rechallenges must be approved by the medical monitor.

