##### **4.2.2. Adherence to Study Drug**

The total number of tablets administered will be summarized using descriptive statistics.

The presumed total number of doses tablets administered to a participant will be determined by the data collected within IXRS for drug accountability using the following formula:

$$\text{Total Number of Doses Administered} = \left( \sum \text{No. of Doses Dispensed} \right) - \left( \sum \text{No. of Doses Returned} \right)$$

The level of on-treatment adherence to the study drug regimen will be determined by the total amount of study drug administered relative to the total amount of study drug expected to be administered during a participant's actual on-treatment period based on the study drug regimen.

The level of on-treatment adherence will be expressed as a percentage using the following formula:

$$\text{On-Treatment Adherence (\%)} = \left( \frac{\text{Total Amount of Study Drug Administered}}{\text{Study Drug Expected to be Administered on Treatment}} \right) \times 100$$

Where, the amount of study drug expected to be administered on treatment will be derived as 2 x Duration of Exposure to Study Drug, which is defined in [Section 4.2.1](#). Descriptive statistics for the level of on-treatment adherence with the number and percentage of participants belonging to adherence categories (eg, <80%, ≥80 to <90%, ≥90%) will be provided by treatment group for the Safety Analysis Set.

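### Read so that its exception clause has effect, SAP 4.2.1 leaves reduced-dose days out of exposure duration, which shortens reported time on drug and inflates calculated adherence

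*SAP*

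**What the plan says.** SAP 4.2.1 opens with a plain date formula: "Total duration of exposure to study drug will be defined as last dosing date minus first dosing date plus 1". It then qualifies it: the count runs "regardless of any temporary interruptions in study drug administration except for protocol-specified dose holds and/or dose reductions". The result is summarised by treatment group in the Safety Analysis Set, with cumulative counts of participants "exposed through the following time periods: 1 day, 3 weeks, 6 weeks, 9 weeks, 12 weeks, 15 weeks, 18 weeks, and >18 weeks".

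SAP 4.2.2 reuses this quantity: "the amount of study drug expected to be administered on treatment will be derived as 2 x Duration of Exposure to Study Drug". The numerator of the adherence percentage is doses dispensed minus doses returned, with no exclusion for reduced-dose periods. Adherence is then grouped, with 80% and 90% as example cut-points.

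SAP 4.2 also promises a summary of "the percent of study drug dose received as specified in the protocol".

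On dose changes, Protocol 6.2 states: "A dose reduction of up to 75% of the original assigned dose is permitted in a stepwise reduction". Its example is that "a dose reduction of up to 50% is allowed and then another reduction to 25% of original dose level may occur". Protocol 4.4 sees in such reductions an opportunity for de facto "exploration of 3 additional dosages (i.e., 5 mg BID, 10 mg BID, and 40 mg BID) in Part 1".

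**The concern.** A dose reduction is not an interruption, because the participant keeps taking study drug at a lower level. A rule that sets reductions beside holds, as exceptions to counting through, treats time on drug as time off drug. It also works back to front: an unplanned lapse with no drug counts as exposure, while a period of reduced dosing does not.

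Two reported quantities are at stake. Duration of exposure would be too short for anyone with a reduction, and she could drop out of the 3-week category. Adherence would be too high for the same participant, because doses taken on the uncounted days stay in the numerator. The rule also fits poorly with Protocol 4.4, which wants to learn from the reduced dosages: the time spent on them would be missing from the summary of exposure.

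**Working it through.** The plan states no figure for this point, so there is none to reproduce. The check applies the definition to assumed dosing patterns.

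**Inputs from the documents.** Duration = last dosing date − first dosing date + 1 (SAP 4.2.1). Exception for holds and reductions (SAP 4.2.1). Adherence = doses taken ÷ (2 × duration) × 100 (SAP 4.2.2). Reduction levels of 50% and 25% (Protocol 6.2).

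**Assumptions.** Duration is in days when it enters the denominator (SAP 4.2.1 expresses it in weeks; that unit question is separate). A dose means one dosing occasion. The participant is treated for 42 days and takes all 2 × 42 = 84 doses.

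**Single participant, no dose missed**

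| Reduced-dose days | Duration, all dosing days | Duration, exception applied | Adherence, all dosing days | Adherence, exception applied |
|---|---|---|---|---|
| 0 | 42/7 = 6.0 wk | 6.0 wk | 84/84 = 100% | 100% |
| 14 | 6.0 wk | 28/7 = 4.0 wk | 100% | 84/(2 × 28) = 150% |
| 21 | 6.0 wk | 21/7 = 3.0 wk | 100% | 84/(2 × 21) = 200% |
| 28 (14 at 50%, 14 at 25%) | 6.0 wk | 14/7 = 2.0 wk | 100% | 84/(2 × 14) = 300% |

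In the last row, a participant dosed for six weeks is not counted as exposed through 3 weeks.

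**Poor adherence hidden.** Suppose she takes 60% of her doses and spends 21 of the 42 days at a reduced level. Doses taken are 0.60 × 84 = 50.4. With the exception applied, adherence is 50.4/(2 × 21) = 120%, so she falls in the group at or above 90%.

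**A shorter course.** Protocol 4.3.2 expects relatively few participants to stay on treatment beyond 3 weeks. With 21 days of dosing and 7 of them reduced, duration is 14/7 = 2.0 weeks instead of 3.0, and full compliance shows as 42/(2 × 14) = 150%. Long reductions are not needed for the effect to appear.

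**Does the unit of counting matter?** SAP 4.2.2 moves between tablets, doses and amount. Count instead in full-dose equivalents, with 21 full days and 21 at 50%: the numerator is 2 × 21 + 0.5 × 2 × 21 = 63 and the shortened denominator is 2 × 21 = 42, giving 150%. With the 21 reduced days at 25%, it is (42 + 10.5)/42 = 125%. A fully compliant participant exceeds 100% in either unit.

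**Arm level, conditional.** If everyone is on drug for 6 weeks and a fraction p has a 3-week reduction, mean reported duration is 6 − 3p weeks. For p = 10% it is 5.7 and for p = 30% it is 5.1. Two arms with equal time on drug would then differ by 0.6 weeks. These rates are invented for illustration.

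**The case against.** The strongest reply is that the SAP never writes a subtraction. Its only formula is the difference in dates, and since a reduction is not an interruption, the exception may be careless wording that no one would program. The SAP also says that it is based on Protocol Version 1, and its three-arm double-blind Part 1 differs from the two-arm open-label Part 1 in the protocol supplied. What counted as protocol-specified when the sentence was written therefore cannot be checked. This stands as a limit on certainty. It does not rescue the sentence: if holds and reductions are counted through like everything else, the exception does nothing. Two programmers could report 6.0 and 3.0 weeks for the same participant.

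Several stronger conclusions are tempting but go beyond the documents:

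- A reader might infer that participants on a reduced dose count as unexposed. Only their reduced-dose days go uncounted.
- A reader might infer that the less tolerable dose will look less exposed and that dose selection is biased. No reduction rate is given for either dose, and the Part 1 primary endpoints in Protocol 3.1 are adverse events and laboratory abnormalities, not exposure duration.
- A reader might take reduction to be the routine step before stopping. Protocol 6.2 has interruption or reduction offered for intolerability, discourages reduction outside its listed criteria, urges symptomatic treatment of gastrointestinal events first, and allows a return to the original dose.
- A reader might infer that the effect of reductions is shown nowhere. Protocol 10.4.2.1 lists dose at adverse event onset, Protocol 10.4.2 analyses safety by dose received, SAP 9 summarises concentrations by dose received, and SAP 4.2.1 plans an exposure listing. What is missing is a summary of how much of the assigned dose was delivered.

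**Conclusion.** The concern holds as a defect of definition. Under the only reading that gives the exception effect, reduced-dose days leave the exposure duration and the same shortened duration inflates adherence. In the assumed 42-day example with 21 reduced days, the error is 3.0 against 6.0 weeks and 200% against 100%. The size in the trial depends on how many participants are reduced and for how long, which the documents do not say, so any difference between arms is conditional.

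The reach is limited. The primary analysis (SAP 6.1.2), Safety Analysis Set membership (SAP 3.1), the treatment-emergent window (SAP 7.1.5.1) and time at risk for exposure-adjusted incidence rates (SAP 7.1.7) do not use this duration. The exposure and adherence summaries are descriptive. The change should be made because it is cheap and the reported figures would otherwise be wrong or would depend on the programmer; it does not threaten the trial's inference.

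**What to change.** In SAP 4.2.1, delete the words and/or dose reductions, so that every day on which study drug is taken counts as exposure whatever the dose level. Hold days may stay excluded. In SAP 4.2.2, use that duration in the denominator.

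Optionally, to deliver the percentage of dose received that SAP 4.2 promises, report the dose level taken as a percentage of the assigned level, with the number of participants reduced to 50% and to 25% by arm. For 21 full days and 21 days at 50% with no dose missed, this is (21 + 0.5 × 21)/42 = 75%, beside an adherence of 100%. Use dose-level or capsule equivalents, not milligrams: a ratio in milligrams is 0/0 for placebo, and dose modifications in Part 2 are blinded.

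The cost is one phrase removed and, if wanted, one derived variable. Protocol 6.6 already requires accountability at capsule level, and the listing of dose at adverse event onset already needs the dose level, so no new data collection appears necessary. Dosing rules and trial conduct are untouched.
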